4.5.7. Physical Examination Variables

Physical exam assessments will be described as normal or abnormal.

4.5.8. Neurological Examination Variables

Neurological evaluations of specific domains as listed in the protocol will be described as normal or abnormal.

4.5.9. Other Safety Variables

Survey of Autonomic Symptoms questionnaire: number of patients reporting health symptoms during the past 6 months for each symptom/health problem assessed as well the severity of symptoms reported at each scheduled visits.

Joint Pain Questionnaire: number of patients with pain in joints lasting more than 2 weeks at each scheduled visits.

Pregnancy on study will be assessed.

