3. STUDY DESIGN

3.1. Study Description and Duration

The study consists of a screening period of up to 30 days (day -37 to day -8), a 7-day pre-randomization period (day -7 to day -1), a 16-week randomized, double-blind, placebo-controlled treatment period (to day 113), and a 20-week follow-up period (Figure 1). Approximately 800 patients will be randomized in a 1:1:1:1 ratio to one of the following 4 treatment groups:

- Fasinumab 6 mg SC Q4W and placebo 9 mg IV every 8 weeks (Q8W)
- Fasinumab 9 mg SC Q4W and placebo 9 mg IV Q8W
- Fasinumab 9 mg IV Q8W and placebo SC Q4W
- Placebo SC Q4W and placebo 9 mg IV Q8W

Randomization will be stratified by baseline LBPI NRS score (<7 , ≥ 7), duration of chronic back pain (<5 years, ≥ 5 years), and maximum Kellgren-Lawrence (K-L) score (≤ 2 , >2) at any knee or hip joint at screening.

- **Screening Period (up to 30 days before the pre-randomization visit):** After informed consent has been signed, patients will be screened for eligibility for enrollment based on study eligibility criteria (Section 4). A magnetic resonance imaging (MRI) of the lumbar spine will be performed during screening. A lumbar spine anterior-posterior/lateral X-ray must be obtained if the MRI of the lumbar spine shows evidence suggestive of a destructive or unstable process. X-rays of the knees, hips, and shoulders will be performed during the screening period. After the patient has otherwise met study eligibility criteria assessed during the screening period, an MRI will be performed and assessed by the central reader prior to the pre-randomization visit for any screening radiographs that are inconclusive for potential joint-related findings and for any knee or hip joints that have a K-L score of ≥ 3 . During the screening period, patients may continue to take their current treatment regimen for LBP.
- **Pre-Randomization Period (7 days before the randomization/baseline visit [day 1]):** Patients who meet the initial eligibility criteria, as assessed during the screening period, will be instructed in the use of the electronic diary (EDiary) for recording daily use of rescue medication and LBPI score using the NRS.

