6. STUDY SCHEDULE OF EVENTS AND VISIT DESCRIPTIONS

6.1. Schedule of Events

Study assessments and procedures are presented by study period and visit in [Table 1](#) and [Table 2](#). A schedule for follow-up of TJR surgery during the study is presented in [Table 3](#).

Table 1: Schedule of Events – Screening Period Through Week 16

Study Week	Screening Period	Pre-Randomization Period	Treatment						End of Treatment Period	Treatment Period Early Termination Visit
			1	2	4	8	12	16		
Study Day (visit window)	up to -37 to -8	-7 (+3) Pre-Rand Visit	1 Baseline	8 (±1)	15 (±3)	29 (±7)	57 (±7)	85 (±7)	113 (±7)	ET
Visit Number	1	2	3	Ph call 1	4	5	6	7	8	ET
Screening/Baseline:										
Informed Consent	X									
Inclusion/Exclusion	X	X	X							
Genomics sub-study informed consent ¹	X									
Medical History	X									
Medication History	X									
Demographics	X									
Height	X									
Bilateral radiograph of knees, hips and shoulders ²	X									
Lumbar spine MRI ³	X									
MRI of any knee or hip with baseline K-L ≥ 3 ²	X								X	X ⁴
NRS/EDiary training ^{5,7}		X								
Assessment of peripheral or central pain	X									
painDETECT Questionnaire	X									
Randomization			X							
Treatment:										
SC Study Drug Injection ⁶			LOADING DOSE			X	X	X		
IV Study Drug Infusion ⁶			X				X			
Dispense paracetamol/acetaminophen		X	X			X	X	X		
Paracetamol/acetaminophen accountability			X		X	X	X	X	X	X

	Screening Period	Pre-Randomization Period	Treatment						End of Treatment Period	Treatment Period Early Termination Visit
				1	2	4	8	12		
Study Week				1	2	4	8	12	16	
Study Day (visit window)	up to -37 to -8	-7 (+3) Pre-Rand Visit	1 Baseline	8 (±1)	15 (±3)	29 (±7)	57 (±7)	85 (±7)	113 (±7)	ET
Visit Number	1	2	3	Ph call 1	4	5	6	7	8	ET
Concomitant medications	X	X	X	X	X	X	X	X	X	X
Efficacy:										
Reporting Your Pain - patient education brochure ⁷	X	X	X		X	X	X	X	X	
LBPI NRS ⁸	X	X	X		X	X	X	X	X	X
Roland Morris Disability Questionnaire			X		X	X	X	X	X	X
Patient Global Assessment LBP	X		X		X	X	X	X	X	X
MOS Sleep Scale Survey			X		X	X	X	X	X	X
SF-36			X		X	X	X	X	X	X
EQ-5D-5L			X		X	X	X	X	X	X
Safety:										
Weight	X								X	X
Vital Signs ⁹	X	X	X		X	X	X	X	X	X
Physical Examination ¹⁰	X								X	X
Electrocardiogram	X								X	X
Joint Pain Questionnaire	X		X		X	X	X	X	X	X
Event-triggered imaging ¹¹					X	X	X	X	X	X
Orthostatic blood pressure	X	X	X		X	X	X	X	X	X
Survey of autonomic symptoms	X		X			X	X	X	X	X
Neurologic examination	FULL		BRIEF		BRIEF	BRIEF	BRIEF	BRIEF	FULL	FULL

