7.4.1.2. Sympathetic Nervous System Dysfunction

Sympathetic nervous system dysfunction will be monitored throughout the study through physical examination, AE monitoring, assessment of orthostatic hypotension, and the Survey of Autonomic Symptoms (Section 6.3.3.5). New onset or worsening of signs and symptoms of autonomic dysfunction will be evaluated by the investigator.

In cases where new or worsening symptoms consistent with sympathetic nervous system dysfunction are moderate to severe or are clinically-significant and do not resolve or return to baseline in 2 weeks (or less at the discretion of the investigator), study drug will be withheld and the patient should be referred to a specialist. If the evaluation by the appropriate specialist does not suggest sympathetic nervous system dysfunction, study drug may be restarted.

If a patient is determined to have orthostatic hypotension, study drug should be withheld and the AE should be entered in the eCRF.

If the patient is symptomatic and a clinical explanation for orthostatic hypotension is identified (such as a new medication or dehydration due to exercise or illness, or excessive heat exposure), study drug should be withheld, and the patient should return to the study site for an unscheduled visit in 1 to 10 days for an unscheduled assessment of orthostatic hypotension. If orthostatic hypotension has resolved, study drug may be restarted. If the orthostatic hypotension has not resolved, then study drug should be withheld, and the patient should be referred to a specialist (neurologist or a cardiologist) for evaluation of sympathetic nervous system dysfunction. If the specialist's evaluation does not reveal new onset sympathetic nervous system dysfunction including symptoms of bradycardia (lightheadedness), orthostatic hypotension (lightheadedness on standing), syncope, or absence of sweating in conditions where sweating would be expected, then study drug can be given at the next visit. If the specialist's evaluation does reveal sympathetic nervous system dysfunction, then study drug will be permanently discontinued.

If the patient has asymptomatic orthostatic hypotension, study drug should be withheld, and the patient should return to the study site for an unscheduled visit in 1 to 10 days for an unscheduled assessment of orthostatic hypotension. If the unscheduled assessment does not reveal orthostatic hypotension, then study drug may be continued. If the unscheduled assessment demonstrates

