5.8. Analysis of Safety Data

The analysis of safety and tolerability will be performed on the SAF, as defined in [Section 3.3](#). The safety analysis will be based on the reported AEs and other safety information (clinical

laboratory evaluations, vital signs, physical exam and 12-lead ECG). Thresholds for Potential Clinically Significant Values (PCSV) in laboratory variables, vital signs and ECG are defined in [Appendix 10.2](#).

The summary of safety results will be presented for each treatment group.

Period of observation: The observation period will be divided into three segments: pre-treatment, on-treatment, and follow-up period.

- The pre-treatment period is defined as the time from signing the ICF to before the first dose of study drug.
- The on-treatment period is defined as the day from first dose of study drug to 4 weeks after the last dose of SC study drug or 8 weeks after the last dose of IV study drug, whichever is later.
- The Post/Treatment follow-up period is defined as from the end of the on-treatment period+1 day to the end of study visit (week 36).

Unless otherwise noted, summaries of safety variables will use data from the on-treatment period. Listings of safety variables will include data from all periods and values occurring during the pre-treatment and follow-up period will be flagged in the listings.

Day 1 is the first day of investigational product, Day –1 is the day before, and there is no Day 0.

The time interval to detect any on-treatment event or abnormality is the on-treatment period. Data collected outside this interval will be excluded from the estimation of descriptive statistics and identification of abnormalities for laboratory evaluations, ECGs and vital signs. All post-baseline data during the interval will be using in the PCSV analysis including scheduled and unscheduled assessments.

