5.8.8. Analysis Other Safety Variables

Summaries and listings will be provided for the Survey of Autonomic Symptoms and Joint Pain Questionnaire. Arthropathy adjudications based on the imaging data will also be summarized.

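### The autonomic-symptom survey is summarized as raw 6-month-recall counts, with no patient-level new-onset or worsening measure

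*SAP*

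**What the plan says.** SAP 4.5.9 counts the "number of patients reporting health symptoms during the past 6 months for each symptom/health problem assessed". Both this count and how severe the symptoms are will be given visit by visit. On analysis, SAP 5.8.8 says only this: "Summaries and listings will be provided for the Survey of Autonomic Symptoms and Joint Pain Questionnaire". Neither section defines a change from baseline, a new symptom or a worsened one.

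The schedules of events (Protocol 6.1, Tables 1 and 2) place the survey at screening, day 1, weeks 4, 8, 12, 16, 20 and 36, and early termination. SAP 5.8 sets the default for safety data: "Unless otherwise noted, summaries of safety variables will use data from the on-treatment period". That period runs to "4 weeks after the last dose of SC study drug or 8 weeks after the last dose of IV study drug, whichever is later".

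Protocol 3.1 names the survey as a means of monitoring for sympathetic nervous system dysfunction. Protocol 7.4.1.2 states what is being looked for: "New onset or worsening of signs and symptoms of autonomic dysfunction will be evaluated by the investigator".

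**The concern.** The recall period is longer than the treatment it is meant to assess. A patient who had a symptom two months before randomization can truthfully report it at every on-treatment visit, and is then counted exactly like a patient whose symptom began after dosing. The protocol's interest is in the second patient.

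The SAP separates the two elsewhere. Adverse events (5.8.1) and laboratory values (5.8.4) have treatment-emergent rules, ECG findings are reported as newly occurring (5.8.6), and abnormal physical examinations as new-onset (5.8.7). The survey has no such rule, although the data for one are collected before the first dose.

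At stake is how clearly a systematically collected questionnaire can show a difference in new autonomic symptoms. Protocol 1.1 records a class-wide clinical hold over sympathetic nervous system changes in animals, and Protocol 3.1.1 lets the data monitoring committee recommend a halt on such an imbalance, so a clear display is worth having.

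**Working it through.** The plan gives no rate, sample size or power for the survey, so there is no figure of its own to reproduce. Two checks were made.

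**1. Timing**

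Inputs: recall of 6 months, taken as 182 days (SAP 4.5.9); nominal visit days from Protocol 6.1.

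Pre-dose days in the window = 182 − (visit day − 1), with a minimum of 0.

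| Visit | Day | Pre-dose days | Share of window |
|---|---|---|---|
| Week 4 | 29 | 182 − 28 = 154 | 85% |
| Week 8 | 57 | 182 − 56 = 126 | 69% |
| Week 12 | 85 | 182 − 84 = 98 | 54% |
| Week 16 | 113 | 182 − 112 = 70 | 38% |
| Week 20 | 141 | 182 − 140 = 42 | 23% |
| Week 36 | 253 | 0 | 0% |

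The latest end of the on-treatment period, with last doses at the late edge of their windows, is day 85 + 7 + 28 = 120 for SC and day 57 + 7 + 56 = 120 for IV. A survey on day 120 still has 182 − 119 = 63 pre-dose days (35%). So every on-treatment recall window contains pre-dose time. A recall of 180 or 184 days shifts each non-zero count by 2 days and changes no conclusion.

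**2. Effect on the comparison**

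Let b be the proportion of patients with the symptom before dosing, and i the new-onset proportion among the rest. Assume that patients with a pre-dose symptom report it again later.

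- Raw proportion = b + (1 − b)i
- New-onset proportion, as a share of the whole arm = (1 − b)i
- Difference between arms, for either measure = (1 − b)(i_active − i_placebo)

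The term b cancels from the difference. It does not cancel from the ratio or from the variance.

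Inputs: 563 randomized patients (SAP 1) over 4 arms, about 141 per arm. The values i = 4% on placebo and 10% on one active arm, and all values of b, are assumptions. Power is the two-sided 5% normal approximation for two proportions, used here only as a measure of signal against noise.

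| b | Raw, placebo vs active | Raw ratio | New onset, placebo vs active | New-onset ratio | Difference, both measures | Power, raw | Power, new onset |
|---|---|---|---|---|---|---|---|
| 0% | 4.0% vs 10.0% | 2.50 | 4.0% vs 10.0% | 2.50 | 6.0 points | 51% | 51% |
| 2% | 5.9% vs 11.8% | 1.99 | 3.9% vs 9.8% | 2.50 | 5.9 points | 41% | 50% |
| 10% | 13.6% vs 19.0% | 1.40 | 3.6% vs 9.0% | 2.50 | 5.4 points | 23% | 46% |
| 20% | 23.2% vs 28.0% | 1.21 | 3.2% vs 8.0% | 2.50 | 4.8 points | 15% | 42% |
| 30% | 32.8% vs 37.0% | 1.13 | 2.8% vs 7.0% | 2.50 | 4.2 points | 11% | 37% |

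At b = 20% the standard error of the difference is √[(0.232×0.768 + 0.280×0.720)/141] = 5.2 points for raw counts and √[(0.032×0.968 + 0.080×0.920)/141] = 2.7 points for new-onset counts. The excess of 4.8 points is the same, but the noise around it is nearly twice as large with raw counts.

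The window shares in the first table do not enter this calculation. They show that pre-dose symptoms can be counted, not how many are.

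**The case against.** The strongest reply is that the formal analysis of this event of special interest does not rest on the survey. Under SAP 4.5.2 these events are identified by a tick box on the adverse event page, and 5.8.2 presents them as treatment-emergent events, which 5.8.1 defines as having developed or worsened on treatment. Orthostatic hypotension is summarized separately in 5.8.5. All of this stands. A reader might infer that the signal for sympathetic nervous system dysfunction as a whole is diluted; the documents do not support that. The point concerns the survey display only. That display has separate value because it is collected systematically, whereas the adverse event route depends on an investigator judging and recording an event.

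Three other strong readings also fail:

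- A reader might say that every on-treatment answer includes pre-dose symptoms. Every recall window includes pre-dose time; what an answer contains depends on the patient.
- A reader might say that the baseline surveys are ignored. Counts and severity at each scheduled visit, read naturally, place screening and day 1 beside the later visits by arm, and the listings cover all periods. What is missing is the patient-level link.
- A reader might call the comparison biased. Pre-dose symptoms should be balanced by randomization.

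The objection on size also has force. No prevalence is given, and exclusions 16, 17, 18 and 23 in Protocol 4.2.2 remove patients with neuropathy, survey-defined autonomic neuropathy, autonomic failure and orthostatic hypotension, so b may be low. The survey analysis is descriptive, so power is only a yardstick. The survey form is in the study reference manual (Protocol 6.3.3.5), so how severity is anchored at repeat visits cannot be checked here.

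**Conclusion.** The point holds as a limitation of one descriptive safety display. Two parts are certain from the documents: every on-treatment recall window reaches before the first dose, and no patient-level new-onset or worsening measure is defined for the survey. The consequence is a risk ratio pulled toward 1 and more noise around an unchanged absolute excess.

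The amount is conditional. With the assumed 4% and 10% onset rates and 141 per arm, the loss runs from none at zero prevalence, through 9 percentage points of power at 2%, to about 27 points at 20%. It also rests on pre-dose symptoms being reported again at later visits. The change is worth making because it is cheap and matches what the protocol says it is looking for. Nothing here undermines the arm comparison or the adverse event analysis.

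**What to change.** Keep the by-visit counts. Add to SAP 4.5.9 and 5.8.8, for each symptom and overall, by arm, the number and percentage of patients with:

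1. a symptom absent at both screening and day 1 and reported at a later visit;
2. separately, a severity above baseline for a symptom already present.

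Classify each by the visit of first report, on-treatment or follow-up. Add a note that a first report in follow-up may describe a symptom that began on treatment: the week 20 window covers the whole treatment period, and the week 36 window opens at about day 71 (253 − 182). Keep the two counts separate, since the second depends on how the form anchors severity.

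The cost is one derived variable and one table. No new data are needed.

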6.3.3.4. Joint Pain Questionnaire

A joint pain questionnaire will be completed by the patient at the time points indicated in [Section 6.1](#). For each knee, hip, and shoulder joint, the patient will be prompted to indicate if they have experienced pain.

A copy of the assessment is provided in the study reference manual.

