7.4.1. Monitoring Adverse Events of Special Interest

7.4.1.1. Adjudicated Arthropathy

Potential events of adjudicated arthropathy will be monitored via clinical signs and symptoms of worsening joint pain (joint pain questionnaire), AE monitoring, and routine imaging.

Clinically significant worsening of joint pain during the course of this study is defined as worsening of pain in any joint, despite treatment with analgesics which is inconsistent with the normal progression of OA, and that lasts at least 2 weeks (or less at the discretion of the investigator).

If a patient reports an increase in joint pain as described above, then study drug administration will be withheld. Imaging of the affected joint will be performed, as well as any additional imaging deemed appropriate to understand the cause of the worsening pain ([Section 6.3.3.8](#)). The decision to perform imaging after patient reports of worsening joint pain will be documented in the respective CRF page. Images, along with any other radiographic evaluation, will be submitted to the adjudication committee for review ([Section 3.3.2](#)).

If routine imaging suggests adjudicated arthropathy, then study drug administration will be withheld. Any additional imaging deemed appropriate will be obtained. Images, along with any other radiographic evaluation, will be submitted to the adjudication committee for review ([Section 3.3.2](#)).

If the adjudication does not confirm adjudicated arthropathy, study drug may be restarted.

Patients with findings that suggest adjudicated arthropathy will have their dosing terminated and will be referred for orthopedic consultation. If joint replacement is warranted, the site should

make all attempts to complete the pre-operative visit prior to surgery, and at the week 4 and week 20 post-operative study visits (Section 6.2.8 and Section 6.3.3.9). Pre-operative images, along with any other radiographic evaluation, will be submitted to the adjudication committee for review (Section 3.3.2).

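### The Joint Pain Questionnaire is planned only as a raw per-visit count with no baseline-referenced or stated by-joint summary, so it cannot separate persistent from new joint pain and may dilute or mask a difference between arms.

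*SAP*

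**What the plan says.** SAP 4.5.9 gives the only analysis variable for the questionnaire: "number of patients with pain in joints lasting more than 2 weeks at each scheduled visits". SAP 5.8.8 adds: "Summaries and listings will be provided for the Survey of Autonomic Symptoms and Joint Pain Questionnaire". Neither section mentions new onset, worsening, shift or change from baseline, or a breakdown by joint.

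Protocol 7.4.1.1 gives the form its purpose. Potential arthropathy events "will be monitored via clinical signs and symptoms of worsening joint pain (joint pain questionnaire), AE monitoring, and routine imaging". The section then sets out which worsening counts as clinically significant: it is "defined as worsening of pain in any joint, despite treatment with analgesics". Two further conditions are attached, so the worsening must also be one that "is inconsistent with the normal progression of OA, and that lasts at least 2 weeks"; the investigator may accept a shorter duration.

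Protocol 6.3.3.4 describes the content: "For each knee, hip, and shoulder joint, the patient will be prompted to indicate if they have experienced pain". The schedule in Protocol 6.1 places the form at screening, day 1, weeks 2, 4, 8, 12 and 16 (Table 1), weeks 20 and 36 (Table 2), and at early termination.

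**The concern.** The form is there to pick up a change in joint pain, but the planned variable is a level. A patient with lasting knee pain before the first dose counts at every visit for as long as that pain continues, exactly as a patient with new hip pain does. If the count is made per patient over all joints, someone whose pain resolves in one joint and starts in another shows no change.

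Lasting joint pain before dosing is plausible. Randomisation is stratified by maximum K-L score (≤2, >2), and the SAP Overview says that some patients had advanced osteoarthritis. That section also links the partial clinical hold to an adjudicated arthropathy in such a patient, so readers will look closely at any patient-reported joint data by arm.

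The SAP is baseline-referenced elsewhere: adverse events that developed or worsened on treatment (5.8.1), treatment-emergent laboratory abnormalities (5.8.4), newly occurring ECG findings (5.8.6) and new-onset physical examination findings (5.8.7). The questionnaire is handled differently although its baseline is collected.

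**Working it through.** The plan states no figure for this variable, so there is none to reproduce. What follows is illustration. Baseline prevalence, onset rates and persistence are assumptions; only the number randomised comes from the documents.

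**1. Dilution when all baseline pain persists.** Let b be the proportion with lasting joint pain at baseline and r the new-onset rate among the rest. The raw count shows p = b + (1 − b)r. Take r = 5% on placebo and 10% on active, a true ratio of 2.0.

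| b | Placebo | Active | Ratio | Difference (points) |
|---|---|---|---|---|
| 0% | 5.0% | 10.0% | 2.00 | 5.0 |
| 20% | 24.0% | 28.0% | 1.17 | 4.0 |
| 30% | 33.5% | 37.0% | 1.10 | 3.5 |
| 50% | 52.5% | 55.0% | 1.05 | 2.5 |

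For b = 30%: 0.30 + 0.70 × 0.05 = 0.335 and 0.30 + 0.70 × 0.10 = 0.370; 0.370/0.335 = 1.10.

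**2. Loss of precision.** SAP Overview: 563 randomised, so n = 563/4 = 140.75 per arm if the 1:1:1:1 ratio held. Take a larger effect, 5% v 15% (ratio 3.0), two-sided alpha 0.05, with

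power = Φ{[|p1 − p0| − 1.96√(2p̄(1 − p̄)/n)] / √([p0(1 − p0) + p1(1 − p1)]/n)}.

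The new-onset comparison uses n(1 − b) per arm.

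| b | Raw prevalence | Raw ratio | Power, raw | Power, new onset |
|---|---|---|---|---|
| 0% | 5.0% v 15.0% | 3.00 | 80% | 80% |
| 10% | 14.5% v 23.5% | 1.62 | 49% | 76% |
| 30% | 33.5% v 40.5% | 1.21 | 23% | 65% |
| 50% | 52.5% v 57.5% | 1.10 | 13% | 51% |

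The SAP plans no test of this variable. Power serves here only as a measure of how clearly the table could show a difference.

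**3. Masking when existing pain is relieved more on active.** Protocol 1.1 reports that all three IV doses in the knee OA proof-of-concept study improved pain against placebo, so persistence may differ by arm. With persistence s, p = bs + (1 − b)r. Take b = 30%, onset 5% v 10%, and s = 90% on placebo v 75% on active:

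- placebo: 0.30 × 0.90 + 0.70 × 0.05 = 0.270 + 0.035 = 30.5%
- active: 0.30 × 0.75 + 0.70 × 0.10 = 0.225 + 0.070 = 29.5%

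New onset has doubled, yet the raw count is one point lower on active. With these onset rates the arms look equal when persistence differs by 0.05(1 − b)/b, which is 20, 11.7 or 5 percentage points at b = 20%, 30% or 50%.

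**The case against.** Several points on the other side stand.

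- **The trigger is worsening, not new pain.** A reader might infer that new pain is what starts the arthropathy work-up. Protocol 7.4.1.1 says worsening in any joint, which includes one already painful. A table of new onset alone would leave those joints out.
- **Baseline prevalence is unknown.** A reader might infer that existing pain swamps the signal. The documents give no prevalence, and K-L score is a radiographic grade, not a pain rate. The effect runs from nothing upwards.
- **The ratio overstates the loss in step 1.** The raw difference, (1 − b)(r1 − r0), equals the excess of new-onset patients per patient randomised. No excess case disappears, and randomisation stratified by K-L score should balance baseline pain. With equal persistence the cost is therefore precision, not bias. This defence does not cover step 3, because randomisation does not equalise relief after dosing.
- **Baseline may be shown.** Screening and day 1 are scheduled visits, and SAP 5.8 says safety listings cover all periods. But it also makes the on-treatment period the default for summaries. With full dosing that ends at about week 16 (SC week 12 + 4, IV week 8 + 8), so display of pre-dose, week 20 and week 36 counts is not assured. Listings would allow a within-patient comparison only by hand.
- **By-joint output is not excluded.** It is simply not stated.
- **Other analyses cover the risk.** Work-up is triggered per patient at the site. Adverse events, AESIs, joint replacements (also by K-L score) and adjudications have their own summaries in SAP 5.8.1 to 5.8.3 and 5.8.8. A reader might infer that arthropathy detection is impaired; the documents do not support that.

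**Conclusion.** The point holds as a limitation of one supplementary display. The planned summary is raw prevalence per visit, does not separate persistent from new pain, and may dilute or mask a difference between arms. Dilution is nil if no patient has lasting joint pain at baseline. It is substantial on the ratio scale at 20% to 50% baseline prevalence if that pain persists. Masking requires existing pain to be relieved more on active than on placebo. The knee OA result makes that plausible, but the documents do not quantify it for this form. The form itself sits in the study reference manual, so whether it grades pain, or records duration by joint, cannot be settled here.

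The cut-offs also differ: more than 2 weeks in SAP 4.5.9, at least 2 weeks in Protocol 7.4.1.1. One describes a questionnaire count and the other a clinical definition, so this is a small matter, but the passages should be reconciled. Overall this is a cheap improvement of minor severity.

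**What to change.** Add to SAP 4.5.9 and 5.8.8 a summary by arm, per visit and cumulatively to week 36, of:

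- patients and joints with lasting pain in a joint that had none at screening or day 1;
- worsened pain in joints already painful at baseline, if the form grades pain; otherwise a by-joint shift from baseline.

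Keep raw prevalence as context and state that it includes the baseline visit. Say explicitly that the table covers the follow-up visits as well as the on-treatment period. Reconcile the 2-week wording between SAP 4.5.9 and Protocol 7.4.1.1 before deriving the flag, and check on the form that duration is recorded by joint.

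Cost: one derived flag and one extra table, with no new data collection.
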